Figure 1: Biochemical and Cellular Processes Leading to Hereditary Angioedema	30
Figure 2: Overview of Study Design	38

LIST OF ABBREVIATIONS AND DEFINITIONS OF TERMS

Abbreviation or Specialist Term	Definition
ACE	Angiotensin-converting enzyme
ADA	Anti-drug (STAR-0215) antibody
AE	Adverse event
██████	██
aPTT	Activated partial thromboplastin time
AUC	Area under the curve
BMI	Body mass index
C1-INH	C1-esterase inhibitor protein
cHMWK	Cleaved high-molecular-weight kininogen
C _{max}	Maximum drug concentration
CRF	Case report form
CSR	Clinical study report
CRO	Contract research organization
ECG	Electrocardiogram
EDC	Electronic data capture
Fc	Fragment crystallizable
FcRn	Neonatal fragment crystallizable receptor
FIH	First-in-human
FSH	Follicle-stimulating hormone
GCP	Good Clinical Practice
HAE	Hereditary angioedema
HBsAg	Hepatitis B surface antigen
HCV	Hepatitis C virus
HMWK	High-molecular-weight kininogen, the natural substrate of human plasma kallikrein
HRT	Hormone replacement therapy
IB	Investigator's Brochure
ICF	Informed consent form
ICH	International Conference on Harmonisation
IEC	Independent ethics committee
IgG1	Immunoglobulin G1

Abbreviation or Specialist Term	Definition
IRB	Institutional Review Board
IV	Intravenous(ly)
mAb	Monoclonal antibody
MedDRA	Medical Dictionary for Regulatory Activities
NCI	National Cancer Institute
PD	Pharmacodynamics
PK	Pharmacokinetics
PT	Preferred Term
REC	Research ethics committee
SAE	Serious adverse event
SAP	Statistical analysis plan
SC	Subcutaneous(ly)
SOA	Schedule of assessments
SRC	Safety Review Committee
$t_{1/2}$	half-life
TEAE	Treatment emergent adverse event
T_{max}	Time to maximum drug concentration
ULN	Upper limit of normal
WBC	White blood cell
YTE	Tyrosine/threonine/glutamate

1. SYNOPSIS

Name of Sponsor/Company: Astria Therapeutics, Inc.	
Name of Investigational Product: STAR-0215	
Name of Active Ingredient: STAR-0215 is a humanized immunoglobulin G1 (IgG1) kappa light chain monoclonal antibody with a YTE modified fragment crystallizable (Fc) domain	
Protocol Number: STAR-0215-201	
Title of Study: A Phase 1b/2 Single and Multiple Dose Study to Assess the Safety, Tolerability, Clinical Activity, Pharmacokinetics, Pharmacodynamics, and Immunogenicity of STAR-0215 in Participants with Hereditary Angioedema (The ALPHA-STAR Trial)	
Study center(s): Up to 25 sites in the United States and globally	Phase of development: 1b/2
Objectives and Endpoints:	
Primary Objective	Primary Endpoints

 To assess the safety and tolerability of subcutaneous (SC) administration of single and multiple doses of STAR-0215 in participants with Type I or Type II hereditary angioedema (HAE) 	
 Incidence of adverse events (AEs) Changes in vital signs, electrocardiogram (ECG) findings, physical examination findings, and clinical laboratory evaluations
Secondary Objectives	Secondary Endpoints

 To assess the efficacy of SC administration of single and multiple doses of STAR-0215 in participants with Type I or Type II HAE To characterize the pharmacokinetics (PK) of SC administration of single and multiple doses of STAR-0215 in participants with Type I or Type II HAE 	
 Change from baseline in monthly HAE attack rate Incidence of HAE attack severity (mild, moderate, and severe) Duration of HAE attack (shorter than 12 hours, 12 to 24 hours, 24 to 48 hours, and longer than 48 hours) The number of HAE attacks requiring on-demand therapy Time to first HAE attack after first and last dosing Concentration of STAR-0215 and the derived PK parameters

 • To characterize the pharmacodynamics (PD) of SC administration of single and multiple doses of STAR-0215 in participants with Type I or Type II HAE • To assess the immunogenicity of SC administration of single and multiple doses of STAR-0215 in participants with Type I or Type II HAE 	
 • Change in plasma kallikrein activity • Formation of anti-drug (STAR-0215) antibodies
Exploratory Objectives	Exploratory Endpoints

 • To evaluate the impact of STAR-0215 on [REDACTED] of STAR-0215 • To conduct an exploratory assessment of the effect of STAR-0215 on [REDACTED] in participants with Type I or Type II HAE 	
 • Changes from baseline in [REDACTED] related to [REDACTED] STAR-0215 • Changes from baseline in the [REDACTED]

Methodology and Study Design: STAR-0215-201 is a Phase 1b/2, multicenter, single and multiple dose study to assess the safety, tolerability, efficacy, PK, PD, and immunogenicity of STAR-0215 in participants with Type I or Type II HAE.
 
Properly consented participants will undergo screening assessments according to the inclusion and exclusion criteria and immediately enter the Run-In period. During the Run-In period, HAE attack information will be collected to determine if a participant meets the eligibility requirement of experiencing at least 2 HAE attacks during this time period and to establish a baseline prior to STAR-0215 administration. If a participant has an HAE attack during the Run-In period before Day 1 (first dose of STAR-0215), all signs and symptoms of the HAE attack must be resolved before dosing. A washout period for on-demand treatment is not required. The Run-In period may be extended after consultation with the Medical Monitor. In Cohorts 2 and 3, if a participant has an HAE attack immediately before the second dose (Day 84 and Day 28, respectively), signs and symptoms of the HAE attack should be improving per participant report prior to STAR-0215 administration; a washout period for on-demand treatment is not required before the second dose is administered.
 
In Cohort 1, each participant who has completed the Run-In period and is eligible for STAR-0215 administration will receive 1 dose of STAR-0215 on Day 1. When Cohort 1 has completed dosing, the Safety Review Committee (SRC) will review the cohort's cumulative safety data from the Screening/Run-In period through 21 days after dosing. Progression to Cohort 2 dosing will occur if there are no concerning safety signals.
 
In Cohort 2, each eligible participant will receive 2 doses of STAR-0215, the first on Day 1 and the second on Day 84. When 6 participants in Cohort 2 have received Dose 1, progression to dosing of Cohort 3 will begin.
 
In Cohort 3, each eligible participant will receive 2 doses of STAR-0215, the first on Day 1 and the second on Day 28.
	

Provided no safety concerns are noted from a cumulative review of safety data from this study and the ongoing first-in-human (FIH) study (STAR0215-101), [REDACTED] and [REDACTED] may be explored in [REDACTED].

STAR-0215 will be administered SC into the abdomen. There will be 4 participants in Cohort 1, 6 participants in Cohort 2, and 6 participants in Cohort 3. Based on the accumulated safety information and enrollment as continually monitored by the SRC [REDACTED] (Section 9.12), up to 6 additional participants may be added to Cohort 2 and/or Cohort 3 (maximum of 12 participants each in Cohorts 2 and 3) after the first 6 participants in Cohort 3 have been enrolled. The dose regimens and dose levels for each cohort are outlined in the table below. There is no placebo group in this study.

Cohort	Dose 1		Dose 2		# Participants
	STAR-0215 Dose Level (mg)	Dosing Day	STAR-0215 Dose Level (mg)	Dosing Day	
1	450	1	NA	NA	4
2	600	1	300	84	6; up to 12
3	600	1	600	28	6; up to 12

Abbreviations: NA = not applicable.

Study assessments will be performed in all cohorts through 6 months after the last dose of STAR-0215 (Day 168 in Cohort 1, Day 251 in Cohort 2, and Day 195 in Cohort 3). At this time, participants who are willing and eligible to consent can begin participation in the long-term open label extension study (STAR-0215-202). For any participants who do not enroll in the long-term open label extension study, monitoring will be performed through [REDACTED] months after the last dose of STAR-0215 in all cohorts (Day [REDACTED] in Cohort 1, Day [REDACTED] in Cohort 2, and Day [REDACTED] in Cohort 3) through regular contacts and scheduled site visit. Safety assessments (including AEs, vital signs, ECGs, physical examinations, clinical laboratory evaluations, and pregnancy testing), and efficacy, PK, PD, immunogenicity, biomarker, and [REDACTED] may be conducted at scheduled site visits.

Hereditary Angioedema Attack Management:

If a participant experiences HAE attacks during the study, they will be permitted standard-of-care on-demand treatment as prescribed by their physician.

Number of participants (planned):

Up to 28 participants with HAE are planned.

Diagnosis and main criteria for inclusion:

Inclusion Criteria:

1. At least 18 years of age at the time of Screening.
2. Willing and able to read, understand, and sign the institutional review board/independent ethics committee/research ethics committee approved informed consent form.
3. Documented diagnosis of HAE (Type I or II). All of the following must be met:
 - a. Documented clinical history consistent with HAE (e.g. SC or mucosal, nonpruritic swelling episodes without accompanying urticaria).

- b. C1-esterase inhibitor protein (C1-INH) antigen or functional level less than 40% of the normal level. Participants with antigen or functional C1-INH level 40% to 50% of the normal level may be eligible if they also have a C4 level below the normal range and a family history consistent with HAE Type I or II. Testing for C1-INH and C4 will be performed at Screening. Historical test results for C1-INH may be used to confirm eligibility if the screening C1-INH antigen test or functional level or C4 level laboratory values are inconclusive, after discussion with the medical monitor.
- c. Age at reported onset of first angioedema symptoms 30 years of age or younger, or a family history consistent with HAE Type I or II.
- 4. Agree not to receive a dose of any vaccine within 7 days before or after STAR-0215 administration.
- 5. Participants of childbearing potential must have a negative serum pregnancy test at Screening, must be not pregnant or breastfeeding at Screening, and agree to use one of the protocol defined forms of highly effective contraception during the study and for a total of ■ months after the last dose of STAR-0215.
 Note: Participants who are not capable of becoming pregnant (e.g. defined as surgically sterile or post-menopausal), per the protocol, are not required to use any form of contraception during the study.
- 6. Participants capable of producing sperm who have partners of childbearing potential must agree to use one of the protocol defined forms of contraception during the study, unless the participant is azoospermic or their partner is surgically sterile (as defined in the protocol).
- 7. Agree not to donate or store sperm or engage in any other activity intended to produce sperm for the purpose of insemination during the study, unless such sperm were collected before the administration of the first dose.
- 8. Agree not to donate or store eggs or undergo assisted reproductive or fertility treatment during the study and for a total of ■ months after the last dose of STAR-0215.
- 9. Experienced at least 2 HAE attacks during the Run-In period, as confirmed by an investigator based on meeting the protocol-specified definition of an HAE attack.

Exclusion Criteria:

- 1. Any concomitant diagnosis of another form of chronic angioedema, such as acquired C1 inhibitor deficiency, HAE with normal C1-INH (also known as HAE Type III), idiopathic angioedema, or angioedema associated with urticaria.
- 2. Any exposure to an investigational drug or device within 90 days or 5 half-lives (whichever is longer) prior to Screening.
- 3. Exposure to a monoclonal antibody or recombinant protein bearing a Fc domain (such as a soluble receptor-Fc fusion protein) within 5 half-lives prior to Screening.
- 4. Use of therapies prescribed for the prevention of HAE attacks prior to Screening:
 - a. lanadelumab within 90 days
 - b. berotralstat within 21 days
 - c. all other prophylactic therapies, within 7 days
- 5. Any exposure to angiotensin-converting enzyme (ACE) inhibitors or any estrogen-containing medications with systemic absorption (such as hormonal contraceptives or hormone replacement therapy) within 28 days prior to Screening. (Topical estrogens applied externally or intravaginally are allowed, provided the Investigator and Medical Monitor agree that the systemic absorption is minimal and unlikely to have health impacts to the participant.)

6. Any exposure to androgens (e.g. stanozolol, danazol, oxandrolone, methyltestosterone, testosterone) within 7 days prior to Screening.
7. History of chronic viral infection with positive test for HIV or hepatitis B surface antigen. History of hepatitis C virus (HCV) that has not been adequately cured.
8. Active liver disease (e.g. acute or chronic hepatitis B or C, alcoholic or non-alcoholic steatohepatitis).
9. Any of the following liver function test abnormalities: alanine aminotransferase (ALT) above 3 times the upper limit of normal (ULN), or aspartate aminotransferase (AST) above 3 times the ULN, or total bilirubin above 1.5 times the ULN (unless participant has known Gilbert's Syndrome and a total bilirubin > 3mg/dL).
10. History of drug or alcohol abuse in the 12 months before Screening.
11. Participant has ongoing cancer, except for the following: basal cell carcinoma of the skin. Ongoing cancer is defined as requiring therapy or intervention to treat or prevent recurrence/progression of disease.
12. Known sensitivity to the ingredients in STAR-0215.
13. Participant is employed by or is an immediate family member of the Sponsor or study site staff or who is committed to an institution by virtue of an order issued by the judicial or the administrative authorities.
14. Participant has any medical or psychiatric condition that, in the opinion of the Investigator, may compromise their safety or compliance, preclude successful conduct of the study, or interfere with interpretation of the results (e.g. a significant pre-existing illness or other major comorbidity that the Investigator considers may confound the interpretation of study results).

Investigational product, dosage, and mode of administration:

STAR-0215 drug product is supplied as a [REDACTED]. It will be administered in a 300, 450, or 600 mg dose.

Duration of treatment:

Individual participants will receive 1 dose of STAR-0215 (Cohort 1; Day 1) or 2 doses of STAR-0215 (Cohort 2; Days 1 and 84 and Cohort 3; Days 1 and 28).

Duration of study:

The duration of study participation for each participant, including the Screening and Run-In period, is up to [REDACTED] or [REDACTED] days in Cohorts 1, 2, and 3, respectively. The study is composed of 3 periods as follows:

- Screening/Run-In: at least 56 days
- Treatment Period: Individual participants will receive STAR-0215 on Day 1 (Cohort 1), Day 1 and 84 (Cohort 2), or Day 1 and 28 (Cohort 3).
- Follow-up Period: approximately 6 months after the last dose of STAR-0215 (Day 168 for Cohort 1, Day 251 for Cohort 2, and Day 195 for Cohort 3). At this time, participants who are willing and eligible to consent can begin participation in the long-term open label extension study (STAR-0215-202).
- Follow-up Period: For participants who do not enroll in the long-term open label extension study, safety monitoring will be performed through [REDACTED] months after the last dose of STAR-0215 in all cohorts (Day [REDACTED] in Cohort 1, Day [REDACTED] in Cohort 2, and Day [REDACTED] in Cohort 3).

Reference therapy, dosage, and mode of administration:

A reference therapy is not included in this study.

Criteria for evaluation**Safety:**

Safety will be assessed by AEs, vital sign assessments, ECG findings, physical examination findings, and clinical laboratory evaluations, including chemistry, hematology, coagulation, and urinalysis.

Efficacy:

Efficacy will be assessed by weekly collection of investigator-confirmed HAE attacks and accompanying HAE attack information.

Pharmacokinetic:

Blood samples will be collected to measure the concentration of STAR-0215 before and after STAR-0215 administration.

Pharmacodynamic:

Blood samples will be collected to assess plasma kallikrein inhibition associated with STAR-0215 administration.

Immunogenicity Analysis:

Blood samples will be collected to measure anti-drug (STAR-0215) antibodies.

Sample size considerations:

This is the first time STAR-0215 is being administered to participants with HAE. No formal sample size calculations have been performed.

Up to 28 participants will be dosed in this study. This is considered adequate to characterize the safety, tolerability, efficacy, PK, PD, and immunogenicity of STAR-0215.

Statistical methods:

Data will be summarized using descriptive statistics (mean, median, standard deviation, minimum, and maximum) or frequency counts and percentages, as appropriate. Results will be presented by cohort. Details regarding the management of all data and statistical methodology, including an explanation of the analyses of exploratory endpoints and imputation of missing data, will be included in the statistical analysis plan (SAP), which will be finalized prior to database lock.

Interim Analyses

In preparation for future clinical development of STAR-0215 and subsequent study planning, interim analyses of data in accumulating cohorts are planned (see table below). The interim analysis will occur after the [REDACTED] in [REDACTED] reaches the [REDACTED] visit and will include all available data from [REDACTED]. The [REDACTED] interim analysis will occur after the [REDACTED] in [REDACTED] reaches [REDACTED] of STAR-0215 (the [REDACTED] visit) and will include all available data from [REDACTED]. Details of any additional interim analyses that may be conducted as warranted will be specified in the SAP. At each interim analysis the Sponsor will review the accumulated safety, efficacy, PK, PD, and immunogenicity data. If no safety concerns are noted following interim analyses, efficacy, PK, PD, and immunogenicity results may inform the decision to add additional participants to Cohorts 2 or 3 (up to a total of 12 in each) and/or [REDACTED] exploring [REDACTED] and [REDACTED]. All analyses will be predefined in the SAP as applicable.

[REDACTED]	[REDACTED]	[REDACTED]	[REDACTED]
[REDACTED]	[REDACTED] in [REDACTED] reaches the [REDACTED] visit	All available cumulative safety, PK, PD, immunogenicity, and efficacy data through the [REDACTED] visit in [REDACTED] and the [REDACTED] visit in [REDACTED]	
• Potential addition of up to 6 participants to Cohort 2 (maximum of 12 participants total)• [REDACTED] to [REDACTED]• [REDACTED] study [REDACTED]
[REDACTED]	[REDACTED] in [REDACTED] reaches [REDACTED] after [REDACTED] (the [REDACTED] visit)	All available cumulative safety, PK, PD, immunogenicity, and efficacy data through the [REDACTED] visit in [REDACTED] the [REDACTED] visit in [REDACTED], and the [REDACTED] visit in [REDACTED]	
• Potential addition of up to 6 participants to Cohort 2 and/or Cohort 3 (maximum of 12 participants total in Cohorts 2 and 3)• [REDACTED] to [REDACTED]• [REDACTED] study [REDACTED]• Inform Sponsor's decision-making regarding [REDACTED]

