4. INVESTIGATIONAL PLAN

4.1. Overall Study Design

STAR-0215-201 is a Phase 1b/2, multicenter, single and multiple dose study to assess the safety, tolerability, efficacy, PK, PD, and immunogenicity of STAR-0215 in participants with Type I or Type II HAE.

Properly consented participants will undergo screening assessments according to the inclusion and exclusion criteria ([Section 5.1](#) and [Section 5.2](#), respectively) and immediately enter the Run-In period. During the Run-In period, HAE attack information will be collected to determine if a participant meets the eligibility requirement of experiencing at least 2 HAE attacks during this time period and to establish a baseline prior to STAR-0215 administration. If a participant has an HAE attack during the Run-In period before Day 1 (first dose of STAR-0215), all signs and symptoms of the HAE attack must be resolved before dosing. A washout period for on-demand treatment is not required. The Run-In period may be extended after consultation with the Medical Monitor. In Cohorts 2 and 3, if a participant has an HAE attack immediately before the second dose (Day 84 and Day 28, respectively), signs and symptoms of the HAE attack should be improving per participant report prior to STAR-0215 administration; a washout period for on-demand treatment is not required before the second dose is administered.

In Cohort 1, each participant who has completed the Run-In period and is eligible for STAR-0215 administration will receive 1 dose of STAR-0215 on Day 1. When Cohort 1 has completed dosing, the SRC will review the cohort's cumulative safety data from the Screening/Run-In period through 21 days after dosing. Progression to Cohort 2 dosing will occur if there are no concerning safety signals. Details of the SRC's review are provided in [Section 4.2](#).

In Cohort 2, each eligible participant will receive 2 doses of STAR-0215, the first on Day 1 and the second on Day 84. When 6 participants in Cohort 2 have received Dose 1, progression to dosing of Cohort 3 will begin.

In Cohort 3, each eligible participant will receive 2 doses of STAR-0215, the first on Day 1 and the second on Day 28.

Provided no safety concerns are noted from a cumulative review of safety data from this study and the ongoing FIH study (STAR0215-101), [REDACTED] and [REDACTED] may be explored in [REDACTED] would be added through an amendment to the protocol.

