5.2. Exclusion Criteria

A participant who meets any of the following criteria will be excluded from this study:

1. Any concomitant diagnosis of another form of chronic angioedema, such as acquired C1 inhibitor deficiency, HAE with normal C1-INH (also known as HAE Type III), idiopathic angioedema, or angioedema associated with urticaria.
2. Any exposure to an investigational drug or device within 90 days or 5 half-lives (whichever is longer) prior to Screening.
3. Exposure to an mAb or recombinant protein bearing an Fc domain (such as a soluble receptor-Fc fusion protein) within 5 half-lives prior to Screening.
4. Use of therapies prescribed for the prevention of HAE attacks prior to Screening:
 - a. lanadelumab within 90 days
 - b. berotralstat within 21 days
 - c. all other prophylactic therapies, within 7 days
5. Any exposure to angiotensin-converting enzyme (ACE) inhibitors or any estrogen-containing medications with systemic absorption (such as hormonal contraceptives or hormone replacement therapy [HRT]) within 28 days prior to Screening. (Topical estrogens applied externally or intravaginally are allowed, provided the Investigator and Medical Monitor agree that the systemic absorption is minimal and unlikely to have health impacts to the participant.)
6. Any exposure to androgens (e.g. stanozolol, danazol, oxandrolone, methyltestosterone, testosterone) within 7 days prior to Screening.
7. History of chronic viral infection with positive test for HIV or hepatitis B surface antigen (HBsAg). History of hepatitis C virus (HCV) that has not been adequately cured.
8. Active liver disease (e.g. acute or chronic hepatitis B or C, alcoholic or non-alcoholic steatohepatitis).
9. Any of the following liver function test abnormalities: alanine aminotransferase (ALT) above 3 times the upper limit of normal (ULN), or aspartate aminotransferase (AST) above 3 times the ULN, or total bilirubin above 1.5 times the ULN (unless participant has known Gilbert's Syndrome and a total bilirubin < 3 mg/dL).
10. History of drug or alcohol abuse in the 12 months before Screening.
11. Participant has ongoing cancer, except for the following: basal cell carcinoma of the skin. Ongoing cancer is defined as requiring therapy or intervention to treat or prevent recurrence/progression of disease.
12. Known sensitivity to the ingredients in STAR-0215.

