7.2. Screening/Eligibility

All screening evaluations must be completed and documented by the Investigator within the specified Screening and Run-In period (refer to the SOAs in [Section 1.1](#)). The Investigator will confirm the participant's eligibility before STAR-0215 administration on Day 1.

Screen failures are defined as participants who provide informed consent to participate in the clinical study but who do not meet the eligibility criteria for participation in this study. Individuals who do not meet the criteria for participation in this study may be rescreened once, provided the reason for screen failure is considered transient and likely to change before rescreening and after consultation with the Medical Monitor. If a participant is rescreened within 28 days of the date of screen failure, the following screening assessments do not need to be repeated unless they were the cause of the screen failure: chemistry, hematology, and virus serology laboratory evaluations. Screening laboratory evaluations may be repeated at the discretion of the Investigator.

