8.7. Medical Safety Monitoring

8.7.1. Medical Monitor

The study Medical Monitor has medical authority to evaluate the safety aspects of the clinical study and may be a Sponsor representative or a representative of a CRO if this obligation is transferred. Investigators may contact the Medical Monitor with specific medical questions on the study protocol, participant eligibility, or for discussion of AEs. Contact information for the Medical Monitor will be provided separately.

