## 2 STUDY DESIGN

### 2.1 Introduction

STAR-0215-201 is a multicenter, single- and multiple-dose study to assess the safety, tolerability, clinical activity, PK, PD, and immunogenicity of STAR-0215 in participants with Type I or Type II HAE. STAR-0215 is a humanized IgG1 kappa light mAb, designed to be a highly potent and specific inhibitor of plasma kallikrein, with a YTE-modified Fc domain to enable delayed clearance and prolonged time in circulation. The study design is a standard approach to the evaluation of the safety and tolerability of an investigational product.

Properly consented participants will undergo screening assessments according to the inclusion and exclusion criteria (Protocol Section 5.1 and Section 5.2, respectively) and immediately enter the Run-In period. During the Run-In period, HAE attack information will be collected to determine if a participant meets the eligibility requirement of experiencing at least 2 HAE attacks during this time period and to establish a baseline prior to STAR-0215 administration. If a participant has an HAE attack during the Run-In period before Day 1 (first dose of STAR-0215), all signs and symptoms of the HAE attack must be resolved before dosing. A washout period for on-demand treatment is not required. The Run-In period may be extended after consultation with the Medical Monitor. In Cohorts 2 and 3, if a participant has an HAE attack immediately before the second dose (Day 84 and Day 28, respectively), signs and symptoms of the HAE attack should be improving per participant report prior to STAR-0215 administration; a washout period for on-demand treatment is not required before the second dose is administered.

In Cohort 1, each participant who has completed the Run-In period and is eligible for STAR-0215 administration will receive 1 dose of STAR-0215 on Day 1. When Cohort 1 has completed dosing, the [Safety Review Committee \(SRC\)](#) will review the cohort's cumulative safety data from the Screening/Run-In period through 21 days after dosing. Progression to Cohort 2 dosing will occur if there are no concerning safety signals. (Protocol Section 4.2)

In Cohort 2, each eligible participant will receive 2 doses of STAR-0215, the first on Day 1 and the second on Day 84. [REDACTED]

In Cohort 3, each eligible participant will receive 2 doses of STAR-0215, the first on Day 1 and the second on Day 28.

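### Synopsis exclusion 9 reverses the Gilbert's syndrome bilirubin exception (> 3 mg/dL, against < 3 mg/dL in Section 5.2)

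*Protocol*

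**What the plan says.** The exclusion criteria appear twice in the protocol: in the Synopsis (Section 1) and in Section 5.2. Item 9 sets the same liver limits in both places: ALT or AST above 3 x ULN, or total bilirubin above 1.5 x ULN. Both then lift the bilirubin limit for known Gilbert's syndrome, subject to a condition on the bilirubin value.

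- Synopsis, exclusion 9: "a total bilirubin > 3mg/dL".
- Section 5.2, exclusion 9: "a total bilirubin < 3 mg/dL".

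Section 5.2 is mandatory: "A participant who meets any of the following criteria will be excluded from this study". Protocol Section 4.1 and SAP Section 2.1 both name protocol Sections 5.1 and 5.2 as the criteria for screening. The synopsis heads its eligibility list "Diagnosis and main criteria for inclusion", yet it prints all 14 exclusions. No clause says which text prevails when the two differ. The schedules of assessments and the SAP do not restate the Gilbert's limit.

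**The concern.** Both versions are current protocol text, so this is not a difference between an amendment log and the text that replaced it. The synopsis version is also illogical on its own terms: it refuses the milder elevations and accepts the higher ones without a ceiling.

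The criterion is a liver-safety threshold. Section 2.5 lists hepatic sinusoidal hypertrophy among the potential risks, and this is the first study of STAR-0215 in people with HAE. (Section 2.1.4.3 reports that finding only in rats, at the top dose, and judges it non-adverse.)

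Because the synopsis prints every exclusion, it can be taken for a complete screening list. Up to 25 sites share up to 28 participants, so many sites will screen very few people. A site working from the synopsis alone could dose someone whom Section 5.2 bars, or reject someone whom it allows. The second error is the harder one to see afterwards, because a rejected candidate may never prompt a query.

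**Working it through.** No sample size, power or error-rate figure is involved. The check is to apply each version of the rule to every possible bilirubin value.

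**Inputs**

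- General limit: total bilirubin above 1.5 x ULN (Synopsis and Section 5.2, item 9; same in both).
- Exception, Synopsis: known Gilbert's syndrome and bilirubin > 3 mg/dL.
- Exception, Section 5.2: known Gilbert's syndrome and bilirubin < 3 mg/dL.
- ULN for total bilirubin: not given (Section 7.9 leaves reference ranges to the laboratory). Assumed here to be 1.0 to 1.3 mg/dL.

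**Rule**

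Excluded if b > 1.5 x ULN, unless the participant has known Gilbert's syndrome and b meets the stated condition. Here b is total bilirubin in mg/dL.

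**Decisions for a person with known Gilbert's syndrome who meets all other criteria**

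| Total bilirubin b | Section 5.2 | Synopsis alone | Both lists applied |
|---|---|---|---|
| b ≤ 1.5 x ULN | eligible | eligible | eligible |
| 1.5 x ULN < b < 3.0 | eligible | excluded | excluded |
| b = 3.0 | excluded | excluded | excluded |
| b > 3.0 | excluded | eligible | excluded |

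Above 1.5 x ULN the two versions decide oppositely at every value except exactly 3.0 mg/dL, where both strict inequalities fail. For example, at b = 2.5 Section 5.2 admits and the synopsis excludes; at b = 4.0 it is the other way round. Applying both lists waives no value at all, so the exception disappears.

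The conditions < 3 and > 3 can never hold together, whatever the ULN. The ULN matters only to whether the Section 5.2 exception covers anything: it does when 1.5 x ULN < 3.0, that is, when ULN < 3.0 / 1.5 = 2.0 mg/dL. The table assumes this.

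**Size of the affected ranges**

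| Assumed ULN (mg/dL) | 1.5 x ULN (mg/dL) | Band wrongly excluded by synopsis, 3.0 − 1.5 x ULN (mg/dL) | 3.0 mg/dL as a multiple of ULN |
|---|---|---|---|
| 1.0 | 1.50 | 1.50 | 3.00 |
| 1.1 | 1.65 | 1.35 | 2.73 |
| 1.2 | 1.80 | 1.20 | 2.50 |
| 1.3 | 1.95 | 1.05 | 2.31 |

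The range wrongly admitted by the synopsis alone is everything above 3.0 mg/dL.

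**Against the protocol's own grading guide**

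Appendix 2 grades bilirubin with normal liver function tests as Grade 3 at 2.0 to 3.0 x ULN and Grade 4 above 3.0 x ULN. Values above 3.0 mg/dL exceed 2.31 to 3.00 x ULN under the assumed ULNs, so anyone admitted by the synopsis exception would enter at Grade 3 or 4. Section 5.2 can also admit values in the Grade 3 range (above 2.0 x ULN but below 3.0 mg/dL). The difference is that Section 5.2 has a ceiling and the synopsis has none. Appendix 2 describes these values as guidelines.

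**The case against.** The best case against acting is that the governing rule is correct and can be found. Section 5.2 is mandatory, and Section 4.1 and SAP Section 2.1 both point to it. Section 12.8 requires sites to read the whole protocol, and an exception granted only to the higher values announces itself as a slip. A site that notices can go to the Medical Monitor "with specific medical questions on the study protocol, participant eligibility" (Section 8.7.1).

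Other safeguards remain. The ALT and AST limits, exclusion 8 (active liver disease) and exclusion 14 (investigator judgement) are the same in both lists. The investigator confirms "eligibility before STAR-0215 administration on Day 1" (Section 7.2). A site that applies both lists errs towards exclusion, which is over-restrictive but not unsafe. Source data verification (Section 10.2), automated data checks (Section 10.5), the recording of all deviations (Section 12.8) and the by-subject listings of eligibility and deviations (SAP Section 6.3.1) might catch a wrong entry. Screening may also be closed: SAP Section 2.5 says enrollment outpaced expectations, and SAP version 3.0, dated 09Aug2024, adds an analysis for when the first 16 participants complete.

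Most of this stands, and it limits the concern to a site that screens from the synopsis alone. It does not make the synopsis right. None of the other criteria puts back a numerical bilirubin ceiling, and the documents do not show which inequality the case report form or its edit checks use. Whether screening is open affects which part of the fix is urgent, not whether one is needed.

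**Conclusion.** The concern holds. The synopsis states a liver-safety eligibility threshold the wrong way round, and for people with known Gilbert's syndrome and bilirubin above 1.5 x ULN it reverses the Section 5.2 decision at every value except exactly 3.0 mg/dL. That conclusion needs no assumption beyond a ULN below 2.0 mg/dL. The band widths depend on the assumed ULN of 1.0 to 1.3 mg/dL.

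The practical reach is small. The documents do not say how many such people were screened or enrolled, and at most 28 are dosed. No endpoint, sample size or planned analysis changes. One indirect route to the data exists: if an eligibility breach were classed as an important deviation affecting efficacy, PK or PD, SAP Section 4.2 allows that participant's data to be removed, in cohorts of 4 to 12. That is a contingency, not a forecast. The error should be fixed because it concerns safety and costs almost nothing to correct.

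**What to change.** 1. If screening is open or could reopen, send sites a short clarification now that Section 5.2 governs: the Gilbert's exception applies only to total bilirubin below 3 mg/dL.
2. At the next amendment, change > to < in synopsis exclusion 9.
3. Check the screening bilirubin of any enrolled participant with known Gilbert's syndrome and a value above 1.5 x ULN against the < 3 mg/dL rule. If screening has closed, this is the step that matters. The planned eligibility and deviation listings make it a small addition.

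The cost is one character in the synopsis, one site communication and a brief data check. Section 5.2 stays as it is.
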